### 9 Study Monitoring, Auditing, and Inspecting

### 9.1 Study Monitoring Plan

Monitoring by the PI: The PI [name], with assistance from the Co-Is [name], the study lymphedema therapists, and other study staff members, will monitor all the study activities to ensure safety of participants and integrity of the data collection and management. The research team will meet monthly to discuss recruitment, retention, study progress, and any safety concerns. Any potential issues related to the study activities will be discussed and addressed appropriately and timely. Participants will be educated regarding signs and symptoms related to adverse events requiring urgent or emergent medical care. All adverse events will be documented using CTCAE criteria, reviewed by [name], [name], and the Medical Monitor, [name]. Any contributing factors will be reviewed. Strategies to prevent further complications will be developed and implemented. Although adverse events are highly unlikely, should they develop, they will be reported to the Medical Monitor immediately and to the Penn IRB, within the required time window.

### 9.2 Auditing and Inspecting

PI [name] will permit study-related monitoring, audits, and inspections by the Medical Monitor, the Penn IRB, government regulatory bodies, and University compliance and quality assurance groups of all study-related documents (e.g., source documents, regulatory documents, data collection instruments, study data, etc.).

# **10** Ethical Considerations

Although this is an interventional study, foreseeable physical, psychological, financial, legal, or other risks from study participation are believed to be minimal.

# 10.1 Risks

1) Physical: LLLT will be used in the trial. No physical risks (e.g., worsening lymphedema or fibrosis) from using LLLT in individuals with breast cancer-related lymphedema have been reported in the known current literature review. No physical risks from using LLLT were reported in the case studies conducted in individuals with head and neck lymphedema. Subjects will not have any burning sensation, warmth, or any other uncomfortable sensations on the sites treated with low-level laser. Currently, there is no safety data in the population under study. Thus, we will inform participants of reporting any physical damages they have during the course of the study.

2) Psychological: There are no known psychological risks associated with LLLT.

3) Financial: The LLLT will be provided free of charge. Patients may incur gas expenses when driving to the Penn Clinic.

4) Legal: There are no known legal risks.

5) Other: There may be risks that are unknown at this time.

Our planned protections from the above-noted risks are as follows:

1) Physical: Currently, there are no known potential physical risks for being in this study. Given no safety data available in the population under study, the research may involve risks that are currently unforeseeable. To minimize any potential physical risks, the following will be done: a) Participants will be given the study contact phone numbers and emails to ask any questions or to report any unexpected problems if the problems are directly related to the study activities; b) if study staff identify any unanticipated problems, [name], [name], and study lymphedema therapists, as well as the Medical Monitor, [name], will be notified immediately. Appropriate evaluation and timely therapy will be provided to the participants with significant unanticipated issues will remain on the study based on safety consideration; and c) if anyone experiences an adverse event directly related to the study activities that are done for research, they can get reasonable, immediate, and necessary medical care for their adverse events at Penn.

2) Psychological: If study staff identifies participants with significant distress during the course of the study, PI [name], Co-Is [name], and the Medical Monitor, [name], will be notified immediately so that appropriate psychological evaluation and referrals will be made. [name], [name] and the Medical Monitor, [name], will determine if participants with significant psychological issues will remain on study.

3) Financial: The LLLT will be provided free of charge. Patients will incur the expense of gas when driving to the Penn Clinic during study follow-up visits. To offset travel/gas cost, participants will be provided a financial token of appreciation for participation in the study.

4) Legal: There are no known legal risks.

5) Other: Should the team become aware of any additional risks, participants will be notified, and informed consents will be modified to reflect the new information.

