### 3.1.3 Study Intervention Phase and Follow Up Phase

Group 1 (laser group): After completion of the baseline measures, Group 1 participants will be scheduled for LLLT. The LLLT includes receiving LLLT twice a week for 6 weeks (12 sessions). After completion of the 12-sessions of LLLT, participants will be given a) contact information and instructions to call for problems and b) a calendar outlining dates for the 4- and 8-week post-LLLT follow-up data collection. Group 1 participants will need to complete 4 study assessment visits.

Group 2 (wait-list control group): After completion of the baseline measures, Group 2 participants will not undergo the LLLT therapy but will complete all the same study assessments as the laser therapy group, including the baseline, 6-week after the baseline, 10-week and 14-week after the baseline assessments. After the 14-week baseline assessment, they will be offered the same LLLT sessions as the laser group. After completion of the 12-sessions of LLLT, participants will undergo the 4- and 8-week post-laser follow-up data collection. Group 2 participants will need to complete 7 study assessment visits.

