# 7 Safety and Adverse Events

### 8.1 Safety Monitoring

The following strategies will be in place to monitor the safety of participants during the course of the study.

During the course of this study, study staff will monitor any adverse side effects or events when interacting with participants and be trained to report these to the PI's immediately. Common Terminology Criteria for Adverse Events (CTCAE v5.0) will be used to document adverse events of the trial. All of the staff members who are involved in this study will be trained by the PI [name] on how to use CTCAE v5.0.

In addition, participants in this study will be screened against the inclusion and exclusion criteria. Participants will be educated regarding signs and symptoms related to adverse events (e.g., sudden increase in swelling) requiring urgent or emergent medical care.

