### 8.2 Recording of Adverse Events

During each contact with the subject, the trained staff will seek information on adverse events by specific questioning and, as appropriate, by examination. Information on all adverse events will be recorded immediately in the source document, and also in the appropriate adverse event module of the case report form (CRF). All clearly related signs, symptoms, and abnormal diagnostic procedures results should be recorded in the source document.

All adverse events will be reviewed by PI [name] and Study Physicians [name] (Co-Is), and the Medical Monitor, [name] (see 8.6 Medical Monitoring section), any contributing factors will be reviewed, and strategies to prevent further complications will be developed and implemented. [name] will meet with the study staff monthly to evaluate any other safety concerns. Adverse events will be reported to the Penn IRB within the window required by the IRB. If the study staff identify the following unanticipated problems related to the research (e.g., infection in the treated area, sudden increase in swelling), which occur during the study, Drs. [name], [name], and study lymphedema therapists, as well as the Medical Monitor, [name], will be notified immediately. Patients will be referred and receive appropriate and timely treatment. [name] and [name] will determine if participants with adverse events or any unexpected issues will remain on the study based on safety considerations. [name] and [name] as well as the Medical Monitor, [name], will evaluate the relationship of each adverse event to the study procedures. [name], [name], and the Medical Monitor, [name], will make the determination of the relationship of the adverse event to the study procedures (e.g., definitely related, probably related, possibly related, unlikely or unrelated).

The clinical course of each event will be followed until resolution, stabilization, or until it has been determined that the study intervention or participation is not the cause. Serious adverse events that are still ongoing at the end of the study period will be followed up to determine the final outcome. Any serious adverse event that occurs after the study period and is considered to be possibly related to the study intervention or study participation will be recorded and reported immediately.

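### Section 10.1, planned protection 1(a), ties a participant's own report of a problem to its being study-related, which conflicts with the adverse event rules in Section 8.2

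*Combined protocol and SAP*

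**What the plan says.** The protocol describes reporting by participants in several places, and the conditions differ.

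- **Section 10.1 (Risks), planned protection 1(a).** Participants receive phone numbers and e-mail addresses to ask any questions or to "report any unexpected problems if the problems are directly related to the study activities".
- **Section 10.1, earlier paragraph on physical risk.** After noting that there are no safety data in this population, it says "we will inform participants of reporting any physical damages they have during the course of the study". No relatedness condition is attached.
- **Section 3.1.3.** After the 12 laser sessions, Group 1 participants are given "contact information and instructions to call for problems". The Group 2 paragraph has no equivalent.
- **Section 8.1 (Safety Monitoring).** "Participants will be educated regarding signs and symptoms related to adverse events (e.g., sudden increase in swelling) requiring urgent or emergent medical care".

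Section 8.2 (Recording of Adverse Events) sets the rules for staff. On how events are found, it says: "During each contact with the subject, the trained staff will seek information on adverse events by specific questioning and, as appropriate, by examination". On what is then kept, the rule has no relatedness condition: "Information on all adverse events will be recorded immediately in the source document". Named study roles and the Medical Monitor "will make the determination of the relationship of the adverse event to the study procedures", on a scale from definitely related to unrelated. Section 8.5 halts recruitment and study activities once a single event is identified that might have harmed a participant.

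**The concern.** Relatedness is an assessment made after an event has been reported. Item 1(a) places it before the report and gives it to the person least able to make it. Section 1 says lymphedema often worsens with time, while Sections 8.1 and 8.2 name a sudden increase in swelling as a warning sign. A participant with new swelling cannot tell the two apart, and Section 10.1 itself says there may be risks that cannot be foreseen.

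The threshold in item 1(a) is also higher than those of the rules it feeds. Section 8.5 acts on possible harm. Section 8.2 requires a serious event after the study period to be recorded and reported if it is considered possibly related. A participant who follows item 1(a) literally could hold back an event that either rule was written to catch. Timely participant protection and the completeness of the safety record are at stake.

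**Working it through.** The protocol states no figure on this point. The check compares the passages and then uses the visit schedule to find where the participant's own report matters.

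**Step 1: which reporting routes carry a relatedness condition?**

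| Place | Route | Condition |
|---|---|---|
| 10.1, item 1(a) | Participant reports a problem | Direct relation to the study |
| 10.1, item 1(a) | Participant asks a question | None |
| 10.1, earlier paragraph | Participant reports physical damage | None |
| 3.1.3 | Participant calls about problems | None, but Group 1 only, after the sessions |
| 8.2 | Staff ask at each contact | None |

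One route out of five carries the condition, so this is an inconsistency within the protocol. Section 8.2 also settles who judges: study roles and the Medical Monitor "will evaluate the relationship of each adverse event to the study procedures".

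**Step 2: scheduled contacts after baseline, weeks 0 to 14 (Section 3.1.3).**

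- Group 1: 12 sessions + 3 assessments = 15 contacts, or 14 if Visit 2 coincides with the last session.
- Group 2: 3 contacts, at weeks 6, 10 and 14.

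**Step 3: gaps between contacts.** The schedule reproduces the durations in Section 4.4: Group 1, 6 + 8 = 14 weeks; Group 2, 14 + 6 + 8 = 28 weeks.

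| Period | Gaps | Unconditional call instruction written? |
|---|---|---|
| Group 1, laser | Days (twice weekly) | Not needed in practice |
| Group 1, after laser | 4 and 4 weeks | Yes (3.1.3) |
| Group 2, waiting | 6, 4 and 4 weeks | No |
| Group 2, laser | Days (twice weekly) | Not needed in practice |
| Group 2, after laser (Visits 5 to 7) | 4 and 4 weeks | No |
| After the final visit | No planned contact | Group 1: given earlier, no end date stated; Group 2: no |

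In Group 2, 6 + 4 + 4 + 4 + 4 = 22 of the 28 weeks lie between widely spaced visits with no call instruction specific to that group. Group 1 has 4 + 4 = 8 such weeks out of 14, and Section 3.1.3 covers them.

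**Step 4: what can be lost?** An event not phoned in should come out when staff ask at the next contact. It can arrive late, be forgotten, or be lost if the participant leaves first. Section 4.5 allows for 20% attrition, 0.20 × 40 = 8 participants. That figure shows that leaving before the next contact is a realistic event. It does not estimate the number of reports lost, and the documents give no basis for such an estimate.

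**The case against.** A reader might infer that participants may report *only* related problems, and that adverse events are therefore filtered before medical review. The documents do not support this. The word *only* does not appear, the contact line in item 1(a) is open to any question, and the same section asks for any physical damage to be reported. Section 8.2 does not rely on calls at all: staff ask at each contact, record everything and pass it to review. This objection stands, and it limits the consequence to what happens between contacts.

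It is also fair to say that the 6-week gap in Group 2 comes before any laser exposure, so an event then cannot be caused by the laser. Under-reporting there would affect the background rate against which Group 1 might be read, but Section 6 plans no formal safety comparison between groups. The gaps that bear on laser safety in Group 2 are the two 4-week intervals after its own treatment.

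The education described in Section 8.1 answers part of the concern. It is framed around signs that need urgent or emergent care, so it does not clearly cover slower or milder problems.

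Finally, Section 10.1 describes what the investigators plan. The participant materials are not among the documents reviewed, so it cannot be said that participants are actually given this wording.

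**Conclusion.** The concern holds as an internal conflict in the reporting rules. Item 1(a) of Section 10.1 sets a relatedness condition that does not fit Section 8.2, the unconditional wording in Sections 10.1 and 3.1.3, or the lower threshold in Section 8.5. It is not a failure of the adverse event collection system.

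The exposure is delay, recall loss or dropout between contacts: up to 6 weeks in Group 2 while waiting, 4 weeks between its visits after laser therapy, and the open period after the final visit in which the plan describes no contact. Group 1's two 4-week gaps are largely covered by its call instruction.

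This rests on three assumptions: that item 1(a) is read literally, that staff question participants at every contact as Section 8.2 says, and that no calls between visits take place beyond those the protocol describes. The number of events affected cannot be estimated. Correction is still worthwhile, because the protocol itself says there are no safety data in this population and because the halt in Section 8.5 can act only on events that have been identified.

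**What to change.** - In Section 10.1, item 1(a), delete the condition that problems be directly related to the study. Say that participants may report any new or worsening problem, whether or not they think it is related.
- In Section 3.1.3, give Group 2 the same unconditional call instruction as Group 1, covering the waiting period as well as the weeks after laser therapy. For both groups, say that it continues after the final visit.
- Check the consent form and other participant materials, and align them if they repeat the clause.
- Leave relatedness to Section 8.2 (Recording of Adverse Events). Sections 8.2 and 8.5 need no change for this point. Item (c) of the same list uses a similar phrase about access to care, which is a separate matter.

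The cost is a few sentences of text and a few more calls about unrelated events. No visit, treatment or analysis changes.

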### 10.2 Benefits

Potential benefits to the individual: Although the potential direct benefit to study participants is unknown, individual participants will be exposed to and have increased knowledge about lymphedema and fibrosis. Participants may have positive feelings about participation in a research program that may benefit others.

Potential benefits to humankind: Possible future benefits for HNC survivors are potentially substantial. If we are able to demonstrate that LLLT is safe, feasible, and effective in HNC patients, we will be adding to the armamentarium of an alternative intervention that can diminish the progression of lymphedema and fibrosis, decrease symptom burden, increase function, and improve overall quality of life.

# 10.3 Risk Benefit Assessment

Currently, there are no known potential risks for being in this study. Given no safety data available in the population under study, the research may involve risks that are currently unforeseeable. As noted above, potential benefits are reasonable and substantial. Thus, based on the risk benefit assessment, it appears to be acceptable for this research within human subjects.

# 10.4 Informed Consent Process / HIPAA Authorization

Once the study is approved by the Penn IRB and the ACC, the trained study team members will meet with potential participants who express interest in the study. Potential study participants will be provided one copy of the informed consent to read and review. Study team members will review the study procedures and activities with potential participants. The informed consent document will be written in lay language and cover all study activities participants will engage in during the study, define the length of time the study will be conducted, and provide instructions for participant withdrawal from the study should they choose to do so. Study staff will review and, when necessary, read the informed consent document to potential participants. Participants will be given ample time and opportunity to ask questions, and all questions will be answered by study staff. The consent process will take place in a private location, with a closed door. Once participants have had an opportunity to ask questions, those questions have been answered, and they indicate an interest in participation, they will be asked to sign a written informed consent document as the study staff witnesses. In addition, the participant will be given a copy of informed consent signed by both the participant and study staff. We will not seek waivers of the informed consent process.

### 11 Study Finances

### 11.1 Funding Source

Abramson Cancer Center Early Phase Clinical Research Support (ACC EPCRS).

### 11.2 Conflict of Interest

All of the team members will follow the University of Pennsylvania Policy on Conflicts of Interest Related to Research.

### 11.3 Subject Payments

All participants will be provided with a financial token of appreciation.

For participants in Group 1, if they complete all the study related activities, they will be paid \$135 in total

For participants in Group 2, if they complete all the study related activities, they will be paid \$240 in total

### 12 Benchmarks for Study/Publication Plan

The key benchmark for success of this study is to complete recruitment goals and data collection as scheduled. The information gathered from this study will provide important data for designing a future RCT that tests the efficacy of LLLT on lymphedema in the HNC survivors. Additional benchmarks for success include: 1) dissemination of preliminary findings at professional conferences and 2) submission of articles to peer-reviewed journals.
